The primary objective of the study is to investigate the adjunct effect of online tDCS with cognitive training on specific cognitive domains in stable schizophrenia patients. (i) right after the intervention (ii) whether maintenance effect at 1 month after intervention.

The secondary objective of the study is to probe (i) any effects on affective, psychotic and negative symptoms; (ii) psychosocial functioning, cognitive insight, subjective quality of life (QOL); (iii) the motivation and enjoyment of continuing playing the computerized cognitive training; (iv) the tolerability and adverse events of tDCS among patients with schizophrenia.

Hypotheses:

1. Concurrent cognitive training with online transcranial direct current stimulation(tDCS) will result in greater incremental training effect in specific cognitive domains as compared to cognitive training alone.

2. The cognitive effect in concurrent cognitive training with online tDCS will be maintained over time.
3. tDCS will have no effect on the affective, psychotic or negative symptoms, as compared to the control group(sham stimulation).

Methodology:

Study design

It will be a parallel-group, double-blinded, randomized controlled trial. It will be a 1-week intervention (5-week observation). Subjects will be randomized into two groups:

1. The intervention group- active stimulation of tDCS in ‘online’ mode +cognitive training
2. The control group- sham stimulation of tDCS + cognitive training

Subjects will be blinded to the allocation with group ratio of 1:1. The schedule, environment and equipment used for both groups will be identical. The study will observe the CONSORT guideline.

Study population and recruitment

Recruitment strategies include a convenience sample of patients with stable schizophrenia who will attend Psychiatric Day Hospitals in Tai Po Hospital. Informed consent will be obtained from each eligible subject.

Inclusion criteria: aged 18-65, right handed, understand and speak in Cantonese, diagnosis of schizophrenia meeting the diagnostic criteria of the World Health Organization’s 10th version of the International Statistical Classification of Disease and Related Health Problems (ICD-10). The screening of subjects will be made clinically by the study psychiatrist based on ICD-10.

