Exclusion criteria: 1) History of significant head trauma; 2) active abuse of alcohol or illegal substances; 3) significant neurologic history such as dementia, stroke, seizure, Parkinson’s disease, multiple sclerosis; 4) concurrent use of cognitive-enhancing medications e.g. acetylcholinesterase inhibitors ; 5) documented history of learning disability; 6) implanted with pacemakers, intracranial electrodes, defibrillators; 7) changes in medication regime over the 2 weeks before or during the study period.

Ethical consideration

The study will be performed in accordance with the Declaration of Helsinki (1964). All participants should take part in the study under voluntary basis. Written, informed consent will be obtained from all participants before inclusion in study, which will be submitted to the CUHK-NTEC Clinical Research Ethics Committee for approval. The study will be conducted in the Psychiatric Day Hospital in Tai Po Hospital. Any participant can withdraw from the study at any time point without the need of explanation. It will not affect the usual care of the participant.

Intervention

Within one week, subjects will receive 5 tDCS sessions applied concurrently with cognitive training on 5 consecutive days (a total of 5 sessions, each 20 minutes) . Participants will have 20 minutes of tDCS stimulation concurrently with 20 minutes of computerized cognitive training.

Based on the most recent metanalysis on tDCS in neuropsychological measures schizophrenia, when the number of tDCS session is not fewer than 5 sessions, no direct trend is identified between the amount of tDCS sessions and neuropsychological measures [24] .

Intervention apparatus:

tDCS Apparatus

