tDCS will be applied using the StarStim 8 (NeuroElectrics, Barcelona, Spain). The StarStim8 system consists of a Neoprene head cap with marked positions for electrode placement, a wireless cap-mounted stimulator and a lap-top control computer. tDCS with strength of 2mA for 20 minutes will be applied based on similar previous studies. [40] The stimulation electrode will be applied according to international EEG system 10-20. The anode will be applied at the left dorsolateral prefrontal cortex , which is located at F3; the cathode will be applied at the right dorsolateral prefrontal cortex , which is located at F4. For electrode placement, saline-soaked , 5cm diameter sponge electrodes will be used. The intervention sessions will be conducted in dedicated consultation rooms of the psychiatric day hospital. The rooms are standard consultation rooms with satisfactory sound-proof quality and comfort.

Sham stimulation will be essentially the same setup and procedure, except that the loading protocol will be different. The electric current will ramp up and ramp down, and will stimulate at 0mA for the remainder of the stimulation time. Because it ramps up in the same way as the real stimulation for a short period of time, the subjects will find it difficult to distinguish between the active and sham tDCS. Sham stimulation is generally regarded as an effective blinding technique, especially for those who have never experienced tDCS before[41].

Cognitive Training

All subjects will have ‘online tDCS’ during computerized cognitive training. Each training session lasts for 20 minutes. Subjects will play an app ‘the Peak’ designed by [name] with computerized cognitive training on a hand held portable iPad. The traditional Chinese version with Cantonese instructions will be selected. The progress, the errors and the sum scores will be kept track in the personal profile. Subjects will play a few exercises supplied by the computerized cognitive training in pseudorandomized order within each session.

Randomization procedure

The subjects will be randomly allocated to the intervention group or the control group by a block randomization procedure (1:1 allocation) . The randomization sequence will be generated by an online randomization tool (www.sealedenvelop.com) . A code (either ‘a’ or ‘s’) will be generated for each patient and the code corresponds to whether ‘a’ (active) or ‘s’ (sham) tDCS will be administered.

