Both the assessor and the subjects will be blinded to the procedure. All subjects are assessed by the study psychiatrist who is blinded to the group allocation. Sham stimulation is generally regarded as an effective blinding technique, especially for those who have never experienced tDCS before[41]. All subjects will not be informed of the group allocation neither.

Definitions and Time Point of Measurements

At baseline(T0, at week-0), after the eligibility of the subjects are confirmed and consent to participate is obtained, the following will be assessed 1) clinical and demographic characteristics of the sample include 2) the primary outcome measure and 3) the secondary outcome measures. At completion of the intervention (T1, at week-1), and one month after the intervention (T2, at week-5), the primary and secondary outcome measures of the subjects will be measured.

i.Clinical and Demographic Characteristics

The subject characteristics include age, gender, handedness, years of education and employment status will be collected. Clinical data, including diagnosis, duration of illness, dosage of medications, daily exercise level and insight will be assessed.

ii. Primary Outcome Measure

Cambridge Neuropsychological Test Automated Battery (CANTAB) will be used as the primary outcome measure. [10] CANTAB is a computerized assessment that is automated and does not rely on the assessors' subjective assessment. It has standardized automated test delivery with systematic scoring and automated saving. Practice effects are eliminated with parallel mode and stimuli randomization. It has concurrent validity same as the MATRICS consensus cognitive battery (MCCB). Due to the sensitivity of CANTAB, it can detect effects in small effect size over shorter period of time. Test-retest reliability is > 0.7 , which is consensed opinion for cognitive evaluation in schizophrenia. Computerized CANTAB tasks on specific cognitive domains on paired associates learning, working memory, processing speeds and executive function will be selected.

iii. Secondary Outcomes Measures

Measures on Affective , Psychotic and Negative Symptoms

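### The trial is called double-blinded, but the open allocation code shows the arm to whoever sets up the stimulation, and nothing controls that person's contact with the patient during concurrent training

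*Combined protocol and SAP*

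**What the plan says.** The Study design section states: "It will be a parallel-group, double-blinded, randomized controlled trial". The Randomization procedure section specifies the blind: "Both the assessor and the subjects will be blinded to the procedure". It then identifies the assessor: "All subjects are assessed by the study psychiatrist who is blinded to the group allocation". No operator, technician or trainer is mentioned.

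The same section describes a one-letter code for each patient, where "the code corresponds to whether ‘a’ (active) or ‘s’ (sham) tDCS will be administered". Under tDCS Apparatus, sham follows the active set-up and procedure "except that the loading protocol will be different". The equipment is a head cap, "a wireless cap-mounted stimulator and a lap-top control computer".

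The Intervention section gives five sessions on consecutive days and says: "Participants will have 20 minutes of tDCS stimulation concurrently with 20 minutes of computerized cognitive training". On equal treatment of the arms, Study design promises: "The schedule, environment and equipment used for both groups will be identical". Staff instructions, help and encouragement are not mentioned there or anywhere else.

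**The concern.** Someone has to take the code, choose the matching stimulation protocol and start it. With this code and no masked label, that person knows the arm. Training takes place in the same 20 minutes as stimulation, so the one team member who must know the allocation may also be the one nearest the patient during training.

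Hypothesis 1 concerns the incremental training effect of active over sham stimulation. If patients in one arm were helped or encouraged more, they could train better for reasons unrelated to current. Blinding the patient and the assessor does not close this route, because the difference would arise during the sessions and not at scoring. The visual analogue ratings of motivation and enjoyment are self-reported and more exposed still. No analysis could separate the two sources afterwards, because staff behaviour would be aligned with arm.

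**Working it through.** The plan states no figure on this point, so the check is a comparison of its statements.

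1. **Who is blinded.** Study design uses the label double-blinded. The Randomization procedure names two parties, assessor and subjects. The label and the list agree with each other, but the list leaves out whoever runs the stimulation.

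2. **What the set-up reveals.** The code letter is the initial of the arm, and the loaded protocol differs by arm. Either is enough to tell the person loading it which arm the patient is in. The documents describe no neutral label, no pre-programmed masked file and no separate key-holder.

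3. **When contact could occur.** Stimulation and training fully overlap in every session. The saline-soaked electrodes must be placed and the device started, so there is some staff contact around each session. Whether anyone stays for the 20 minutes is not stated. The stimulator is wireless and laptop-controlled, which fits either arrangement. Safety Consideration promises medical attendance if an adverse effect arises, but does not place anyone in the room.

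4. **What is held equal.** Schedule, environment and equipment are identical, and sham otherwise follows the active procedure. Neither statement scripts what staff say or do.

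5. **Can the effect be sized?** Only by assuming the answer. Take 44 patients at 1:1, so n = 22 per arm, no true tDCS effect, and an assumed staff-induced shift b. For a two-sided 5% two-sample t test, df = 42 and the noncentrality is (b/SD) × √(n/2) = (b/SD) × √11. The documents give no value for b, and its scale is also open:

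| Assumed shift b | b in SDs of the analysed score | b in SDs of the raw score, analysed as change, T0–T1 correlation 0.7 assumed (change SD = √(2 × 0.3) = √0.60) |
|---|---|---|
| 0.1 | 6.2% | 7.0% |
| 0.2 | 9.9% | 13.3% |
| 0.3 | 16.3% | 24.1% |

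The entries are rejection rates. Any bias of the given size, from any source, would produce them. They say nothing about whether this bias occurs, so they are not an estimate of the risk here.

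**The case against.** The strongest reply is that the plan already limits this route.

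- Training is played by the patient on an iPad app with Cantonese instructions. The app supplies the exercises and the order is pseudorandomized. No human trainer is described.
- CANTAB is delivered and scored automatically, so unequal encouragement would have to act through training effort and then carry over to a separate battery at T1, and again a month later at T2.
- Sham is promised the same set-up and procedure apart from the loading protocol.
- All assessments are made by a psychiatrist who is blinded, which largely implies that the operator does not assess.
- Double-blinded with two named parties is not a contradiction.

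All of this stands, and it lowers the risk. It does not remove it: an app standardises the task and not the conversation around it, and automated scoring records a real difference in performance faithfully, whatever caused it.

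Two stronger readings are tempting. A reader might infer that an unblinded operator sits with each patient throughout training, giving 5 × 20 = 100 minutes of one-to-one contact. The documents do not support that. The 100 minutes are session time, and nothing says who is in the room or that anyone coaches. A reader might also quote an inflated false-positive rate as the size of the problem. That too is unsupported, because the rate follows entirely from a shift that the documents do not give.

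**Conclusion.** The concern holds in a conditional form. As written, the blind covers assessor and subjects only, and the open code and the different sham loading protocol reveal the arm to whoever sets up the stimulation. That conclusion assumes only that this person uses the code as described. The further step, that arm-dependent help or encouragement could enter the comparison, also requires that this person attends the concurrent training. The plan neither states nor rules this out.

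The size of any bias cannot be derived from the documents. The point is more than missing detail, because the self-revealing code is a stated procedure that can be changed at almost no cost. It should be settled before the first session, since it cannot be corrected in the analysis.

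**What to change.** In the tDCS Apparatus, Cognitive Training and Randomization procedure sections:

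1. Replace the 'a'/'s' code with neutral labels. Have an existing team member who does not run sessions save the two stimulation protocols under those labels and hold the key.
2. State who operates the device and whether that person stays during training. Limit staff contact in sessions to the app's own instructions plus a fixed script that is the same in both arms, with the laptop screen out of the patient's view.
3. If the operator cannot be masked, for example because the control software shows the current being delivered (the documents do not say whether it does), describe the trial as patient- and assessor-blinded with an unblinded operator. The script in item 2 is then the main safeguard.

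The cost is a one-off set-up, a one-page script and a few sentences of protocol text. No visits, patients or assessments are added, and the stimulation itself is unchanged.

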The baseline demographics and baseline clinical characteristics (T0) will be compared between the group of active tDCS and sham tDCS with Pearson's chi-square test (for categorical variables) and independent-sample t tests (for continuous variables).

Linear mixed effect models will be used for each outcome measures, using the covariates of group (tDCS versus sham) and time (T0, T1 and T2).

Pearson's correlation test will be performed to evaluate whether there will be correlation between change in cognitive performance vs demographics and baseline clinical characteristics.

Statistical significance will be referred to a two tailed p-value of less than 0.05.
All computations will be performed using SPSS for Mac OS and Microsoft for excel.

Data Management:

Raw data and electronic data will be stored in locked space and password protected computers respectively. All data will be destroyed 5 years after completion of study and submission for publication.

Sample size estimation :

The effect in difference found in the specific cognitive domains between the tDCS and sham group before and after the intervention in the similar studies was 0.31 (Smith et al., 2015), 0.21 (Lam, 2016), 0.6 (Nienow et al., 2016) represented by partial eta square. Considering the medium to large effect size of the studies, it is difficult to replicate a study with a large effect size. Hence, the rule-of-thumb medium effect size Cohen's F 0.25 was chosen as the partial eta square. Considering a power of 80% and a critical alpha of 5%, it was estimated that a total of 44 patients would be needed in total. .

Safety Consideration:

Concerning the safety profile, tDCS is generally regarded as safe for short-term administration. There is no published report that tDCS has to be discontinued for safety reasons. The adverse effects of tDCS have been reported to be minimal and its risk of inducing seizure is minimal. Meta-analysis suggested that tDCS is associated with mild adverse effects only, such as itching, tingling, mild burning or pain sensations. [51]In particular, mild burning is related to administration of electric current with higher contact impedance. In our study, we will use the StarStim 8 (NeuroElectrics, Barcelona, Spain). StarStim 8 will not operate if the contact impedance is above 20 kOhm, which is the far from the threshold for tissue damage.

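### Four CANTAB domains are primary, each judged at 5%, with no success rule or multiplicity control; if any one domain suffices, false-positive risk is about 13–18.5% on assumed correlations

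*Combined protocol and SAP*

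**What the plan says.** All references are to the combined protocol and SAP.

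- **Primary Outcome Measure:** "Cambridge Neuropsychological Test Automated Battery (CANTAB) will be used as the primary outcome measure". The tasks are still to be chosen: "Computerized CANTAB tasks on specific cognitive domains on paired associates learning, working memory, processing speeds and executive function will be selected". Four domains are named. The task, the number of tasks and the outcome variable within each domain are not.
- **Statistical Analyses:** "Linear mixed effect models will be used for each outcome measures", with group and time (T0, T1, T2) as covariates. The significance rule is general: "Statistical significance will be referred to a two tailed p-value of less than 0.05". No contrast is singled out.
- **Hypotheses:** Hypothesis 1 predicts that training with active stimulation "will result in greater incremental training effect in specific cognitive domains as compared to cognitive training alone". Hypothesis 2 reads "The cognitive effect in concurrent cognitive training with online tDCS will be maintained over time".
- **Objectives:** the primary objective covers two time points, directly after the intervention and one month later. The later one is worded as maintenance.
- **Sample size estimation:** 80% power, 5% alpha, 44 patients in total. No allowance is made for several domains.

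No section gives a composite, an order of testing, a rule for the number of domains that must succeed, or a multiplicity adjustment. Nothing in these sections is marked as redacted.

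**The concern.** The plan states a primary objective, directional hypotheses and a power calculation, so it makes a confirmatory claim. Yet a reader cannot tell which result would confirm it. Followed literally, each domain has its own model and its own 5% threshold, and any significant domain could be reported as a primary finding.

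Both the error rate and the power depend on the missing rule. An any-one-domain rule raises the false-positive rate well above 5%. An all-four rule makes a false claim very unlikely but success hard to reach. Unless the rule is on record before unblinding, readers cannot distinguish a planned primary result from the best of four.

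**Working it through.** **The plan's own figure.** The plan gives no family-wise error rate. Its only related figure is N = 44, which cannot be uniquely reproduced because the test, number of time points, correlation and sphericity are not stated. One setting that returns it is a two-group, group-by-time F test with f = 0.25, three time points and repeated-measures correlation 0.2. The noncentrality is f² × N × m / (1 − ρ) = 0.0625 × 44 × 3 / 0.8 = 10.31, giving 81% power; N = 42 gives 79%. With correlation 0.5 and sphericity, the same test needs 28 patients (three time points) or 34 (two). In each case this is one test at 5%.

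**Inputs for the error rate.**
- Number of domains, K = 4 (Primary Outcome Measure).
- Level per test, 0.05 two-sided (Statistical Analyses).
- One test per domain: assumed, since the number of scores is not given.
- Between-domain correlation ρ: not in the documents. 0 to 0.7 is assumed, with 0.9 as a stress case.

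**Any-one-domain rule, no true effect.**
- Independent tests, two-sided: 1 − 0.95⁴ = 0.1855.
- Independent tests, favouring active: 1 − 0.975⁴ = 0.0963, against 0.025.
- Equally correlated tests: 1 − ∫ φ(x) [Φ((c − √ρ x)/√(1 − ρ)) − Φ((−c − √ρ x)/√(1 − ρ))]⁴ dx, with c = 1.96. For errors favouring active, the second Φ term is dropped.

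| ρ | Two-sided | Favouring active |
|---|---|---|
| 0 | 18.5% | 9.6% |
| 0.3 | 17.4% | 8.7% |
| 0.5 | 15.6% | 7.8% |
| 0.7 | 13.0% | 6.5% |
| 0.9 | 9.4% | 4.7% |

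Simulated two-sample t tests with 22 per arm give 18.7%, 17.3%, 15.7% and 13.1% at correlations 0, 0.3, 0.5 and 0.7.

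**All-four rule.** The chance that all four domains falsely favour active is at most 0.3% for correlations up to 0.7, and about 0.9% at 0.9.

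**Power under the two rules.** Assume d = 0.5 in every domain (d = 2f for two equal groups with f = 0.25), 22 per arm, a baseline-adjusted T1 contrast, and domain correlation 0 to 0.7. With baseline correlation 0.7, power is 84–98% for any one domain and 15–38% for all four. Over baseline correlations 0.5 to 0.8, the ranges widen to roughly 69% to over 99%, and 4–58%.

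**Effect of Holm across four T1 tests.** With no effect in any domain, a false claim requires at least one p-value below 0.05/4 = 0.0125. The same integral gives 4.9% at ρ = 0 and 3.7% at ρ = 0.7.

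**Power for one domain.** The noncentrality is d√(n/2)/√(1 − r²), with 41 df. At r = 0.7 it is 0.5 × √11 / √0.51 = 2.32.

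| Baseline correlation r | Level 0.05 | Level 0.0125 |
|---|---|---|
| 0.5 | 46% | 26% |
| 0.7 | 62% | 40% |
| 0.8 | 77% | 56% |

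**The case against.** **The plan never says that one domain is enough.** True. A reader might infer that the trial's type I error is 13–18.5%. The documents do not support that as a fact, because the figure belongs to one of several readings they leave open. What stands is that no reading is excluded and that the operating characteristics differ greatly between them.

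**The hypothesis is directional.** The risk that matters most is therefore a false claim for active tDCS, 6.5–9.6% against 2.5%. This is fair. The two-sided figure also counts domains favouring sham, so both are given. If the test turns out to be a group-by-time F test over three visits, direction is not defined by the test itself.

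**Four tests is an inference.** Also fair: the text says tasks, without a number. Several scores per domain would raise the risk. A reader might also count T1 and T2 separately: eight equally correlated tests would give 19–34% at correlations 0.7 to 0. But the protocol frames T2 as maintenance, so that count is not used here.

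**Late selection is hypothetical.** Nothing says the variables or the rule will be chosen after unblinding. The point is only that the plan as written would not prevent it.

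**Conclusion.** The point holds as an undefined success criterion with uncontrolled multiplicity on the primary outcome. It should be fixed before unblinding, since later analysis cannot restore a pre-specified rule.

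The error figures are illustrative. They rest on an any-one-domain reading, one test per domain and an assumed between-domain correlation of 0 to 0.7. Even at 0.9 the two-sided rate is 9.4%. If all four domains must succeed, there is no inflation and the cost falls on power instead.

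A reader might infer from the 62% single-domain power that the trial falls short of its planned 80%. That does not follow: 62% is for a baseline-adjusted T1 contrast at assumed values, and the test behind the plan's 80% is not named.

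**What to change.** Before unblinding, amend the Primary Outcome Measure and Statistical Analyses text:

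1. Name one CANTAB outcome variable for each of the four domains.
2. Name the active–sham contrast at T1 as the primary comparison.
3. Control two-sided 5% error across the primary family. Holm over the four T1 domain tests is closest to Hypothesis 1, with success claimed only for domains that pass. Alternatives are a single named variable, if one key domain is expected, or the mean of four domain z-scores, if a broad effect is expected. The remaining domains would then be secondary.
4. Define the T2 maintenance contrast. Test it only for the domains, or the composite, that succeed at T1, or label it supportive. T2 need not leave the primary objective. If confirmatory T2 claims are wanted in several domains, set their level too. A simple scheme, in place of Holm, gives each domain 0.0125 and carries it from T1 to T2 within that domain (4 × 0.0125 = 0.05).
5. Limit the restriction to cognitive efficacy claims. Tolerability, symptom and functioning outcomes are reported as planned.

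**Cost.** This is a text change with no extra visits and, unless the sponsor wants to restore power, no extra patients. Power per domain falls: about 40% against 62% at the first Holm step on the assumptions above (26–56% against 46–77% for baseline correlation 0.5 to 0.8). Later Holm steps are less strict. In the interaction-test setting that returns 44, using 0.0125 instead of 0.05 would need 60 patients.

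The composite avoids the adjustment but suits a broad effect. At d = 0.5, baseline correlation 0.7 and domain correlation 0.7 to 0, its power is 73% to over 99% if all four domains respond, 25–62% if two do, and 10–21% if only one does.

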- Positive and Negative Syndrome Scale (PANSS) [42] is a 30-item clinician rated questionnaire to assess the symptoms in schizophrenia patient. It has 3 sub-categories of positive symptoms, negative symptoms and general psychopathology. It is shown to have good construct validity , internal reliability and inter rater reliability. [43] It is also shown to be sensitive to change. [44] The assessment time is around 40-50 minutes.
- Calgary Depression Scale for Schizophrenia [45, 46] is a 9-item clinician rated and is administered following a semi-structured interview. It has been used by other tDCS studies in schizophrenia, and it has been shown to be reliable , valid and sensitive to depressive symptoms separate from positive, negative and extrapyramidal symptoms in schizophrenia. A score above 6 has 82% specificity and 85% sensitivity for predicting the presence of a major depressive episode.

- Clinical Global Impression Scale (CGI) [47]- Schizophrenia is a 3-item clinician rated questionnaire to assess illness severity, global improvement or change, and treatment response.

Measures on Psychosocial Functioning

- Social and Occupational Functioning Assessment scale (SOFAS)[48]
- World Health Organization Five Well-Being Index (WHO-5) is a 5-item self reported questionnaire of subjective quality of life (QOL). [49, 50]

Ratings on Motivation and Enjoyment on Cognitive Training

- Visual Analog Scale to rate their motivation and enjoyment to continue playing the computerized cognitive training game (scores ranged from 0-100, with higher scores indicating enhanced enjoyment/ willingness to come)

Tolerability on tDCS

- An Adverse Effects Questionnaire associated with t-DCS administration, which is generated from a systematic review in 2011 by Brunoni. [51]

Clinical Insight

- Beck Cognitive Insight Scale Taiwanese Version is 15-item self reported questionnaire with two subscales (nine items tapping self-reflectiveness and six on self-certainty); it is shown to have Cronbach's alpha values of >0.70 for both subscales and moderate stability.[52, 53]

Statistical Analyses:

The data will be collected according to the Intention-to-treat(ITT) protocol, with last observation carried forward (LOCF) design i.e. all subjects whose baseline data collected and performed at least 1 day of stimulation will be included in the analysis. The missing observation due to non-compliance will be imputed accordingly to the last assessment performed.

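### Under the written rules, a patient who stops tDCS early and also misses T1 can be given a pre-stimulation adverse-effects score, and no reading is tied to a session or to discontinuation

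*Combined protocol and SAP*

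**What the plan says.** The Objectives section of the combined protocol and SAP lists, as a secondary objective, "iv) the tolerability and adverse events of tDCS among patients with schizophrenia". The only instrument named for it is under Secondary Outcomes Measures, Tolerability on tDCS: "An Adverse Effects Questionnaire associated with t-DCS administration". That entry gives no time of administration, no collector and no scoring.

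The section Definitions and Time Point of Measurements supplies the general schedule. Baseline (T0) covers "2) the primary outcome measure and 3) the secondary outcome measures". At T1 (week 1) and T2 (week 5), "the primary and secondary outcome measures of the subjects will be measured". No other assessment time is given. The Intervention section places all five sessions in one week, between T0 and T1.

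Statistical Analyses admits anyone with baseline data and one or more days of stimulation, and states: "The missing observation due to non-compliance will be imputed accordingly to the last assessment performed". It continues: "Linear mixed effect models will be used for each outcome measures", with group and time (T0, T1, T2) as covariates. Neither rule exempts tolerability data.

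Safety Consideration expects mild effects, "such as itching, tingling, mild burning or pain sensations". It provides for on-site medical attendance but describes no recording procedure.

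**The concern.** The effects the plan expects are sensations linked to the current, so they arise during a session. The patients most informative about tolerability are those who stop because of them. Under the general schedule such a patient may have only one questionnaire on file, the one taken before any stimulation. Carrying it forward enters that patient in the analysis as someone whose effects did not change from baseline.

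Two further features weaken the tolerability result. For completers, five sessions are summarised by a single recall at T1. And a linear mixed model of group and time does not give what a reader needs, namely how many patients in each arm had each effect and how many stopped because of it.

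At stake is the answer to a stated secondary objective. Experience that was not recorded at the time cannot be recovered in the analysis.

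**Working it through.** The plan states no tolerability figure to reproduce, so the check is mainly a reading of the rules, followed by a short illustration.

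**1. Which value enters at T1?** Applying the schedule (Definitions and Time Point of Measurements) and the LOCF rule (Statistical Analyses) to a patient with at least one session:

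| Patient | Value analysed at T1 |
|---|---|
| Completes five sessions, attends T1 | Observed T1 value |
| Stops early, still attends T1 | Observed T1 value |
| Stops early, no T1, handled as non-compliance, T0 questionnaire on file | T0 value, before any stimulation |
| Stops early, no T1, not handled as non-compliance | No rule stated |
| Stops early, no T1, no T0 questionnaire taken | Nothing to carry forward |

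Only the third row produces a false value. In the last two rows the patient's experience is simply absent. The direction of bias applies to a missed T1: if T1 is attended and T2 missed, the value carried forward was taken after stimulation.

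**2. Does another provision capture the experience?** Ethical consideration allows withdrawal at any time without a reason and describes no assessment at that point. Safety Consideration describes attendance by a medical professional, not recording. No session-level rating, adverse-event log or count by arm is described.

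**3. Size per patient.** Inputs: 44 patients in total (Sample size estimation) and 1:1 allocation (Randomization procedure).

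- Per arm: 44 / 2 = 22.
- Effect on an arm's rate of one patient with an effect who is recoded as having none: 1 / 22 = 4.5 percentage points.

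This uses the proportion of patients with an effect, which the plan itself does not define, and assumes the T0 value shows no effect.

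**4. Illustration with assumed counts.** Suppose 11 of 22 active patients and 6 of 22 sham patients truly have an effect, and x active patients with effects fall in the third row of the table.

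- True difference: 11/22 − 6/22 = 5/22 = 22.7 points.
- Analysed difference: (11 − x)/22 − 6/22 = (5 − x)/22.

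| x | Analysed difference (points) |
|---|---|
| 0 | 22.7 |
| 1 | 18.2 |
| 2 | 13.6 |
| 3 | 9.1 |
| 5 | 0.0 |

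With 15 active and 8 sham patients instead, the true difference is 7/22 = 31.8 points (Fisher exact p = 0.069). With x = 3 it is 4/22 = 18.2 points (p = 0.364).

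If equal numbers in both arms were recoded, the difference would be unchanged but both rates would be understated. All counts here are assumptions; none comes from the documents.

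**The case against.** The strongest reply is that the plan has a gap rather than a wrong rule.

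- **Timing.** The questionnaire has no schedule of its own, and its description would fit use after each session. That it is taken only at T0, T1 and T2 is an inference from the general schedule. This stands: undocumented session-level use cannot be excluded. If it is intended, the protocol should say so.
- **The T0 value.** A questionnaire about effects of stimulation makes doubtful sense before any stimulation, and its items are not given. If it is not taken at T0, nothing is carried forward. This also stands, but the early stopper's experience is then lost instead of miscoded.
- **Early stopping is not loss to follow-up.** A reader might infer that every patient who stops early is scored with the pre-stimulation value. The documents do not support that: T1 must also be missing, and nothing says that stopping stimulation ends assessment.
- **Scope of LOCF.** The rule covers data missing through non-compliance. Whether stopping for side effects counts is not stated, and no other rule is offered for such data.
- **Unblinding.** Because "All subjects are assessed by the study psychiatrist who is blinded to the group allocation", a reader might infer that collecting side-effect reports unblinds the clinician-rated scales. The documents do not say who administers this questionnaire, and the sham ramps up in the same way as active stimulation. That claim is not supported.
- **Frequency.** The plan expects only mild effects, so dropouts of this kind may be few. A withdrawal would also remain visible as a withdrawal, whatever score was imputed. Both points are fair; they limit the size, not the direction.

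These points make the problem conditional. They do not remove it, since no provision in the plan prevents the sequence.

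**Conclusion.** The point holds in conditional form. Four conditions must coincide: at least one session received, stimulation stopped, no T1 assessment, and the missing value handled as non-compliance with a T0 questionnaire on file. Following the written rules then assigns a value that cannot contain a stimulation effect, and the tolerability result is biased towards safe. Each such patient with an effect costs about 4.5 points of that arm's rate at 22 per arm. How many there would be, and whether they would fall mainly in the active arm, is not known from the documents, so no overall bias can be stated.

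Independently of those conditions, the plan ties no reading to a session or to discontinuation, and the planned model does not yield counts by arm. It would go too far to say that the tolerability conclusion will be wrong or that session-level data will certainly not exist. The change should be made before recruitment, because it concerns data collection as well as analysis.

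**What to change.** **Collection.** State in the protocol that the questionnaire is given after each of the five sessions and at discontinuation, keeping T0 as a symptom baseline and T2 for late effects. Name the staff already running the session as collectors. This last step is a sensible precaution for blinding, not a response to a demonstrated breach. Since participants may withdraw without explanation, allow for a reason not given.

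**Analysis.** Exclude the questionnaire from LOCF and from the linear mixed model. Among all patients who received any stimulation, report by arm:

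- the number and percentage with each effect, by worst severity;
- the number who discontinued because of side effects;
- an exact confidence interval for the between-arm difference.

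**Cost.** A few minutes of added patient burden per session with staff already present, and short wording changes to the schedule and the Statistical Analyses section. No stimulation or clinical rule changes.
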